**12. PHARMACODYNAMIC ANALYSES**

No pharmacodynamics analyses are planned for this study, but the pharmacodynamic data may be used for a separate report.

**13. PHARMACOKINETIC / PHARMACODYNAMIC ANALYSES**

No pharmacokinetic / pharmacodynamic analyses are planned for this study, but the pharmacokinetic / pharmacodynamic data may be used for a separate report.

## 15. APPENDICES

### 15.1. Appendix 1: Protocol Deviation Management and Definitions for Per Protocol Population

#### 15.1.1. Exclusions from Per Protocol Population

A subject meeting any of the following criteria will be excluded from the Per Protocol population:

Number	Exclusion Description
01	Informed Consent in Deviation Category
02	Eligibility Criteria Not Met in Deviation Category
03	Not Withdrawn After Developing Withdrawal Criteria in Deviation Category
04	Wrong study treatment or assignment administered in Deviation Subcategory
05	Randomization procedures (e.g. subject randomized out of order) in Deviation Subcategory
06	Less than 3 out of 4 scheduled evaluable Hgb values from the primary efficacy evaluation period 
07	Subject received prohibited medication for more than 14 days during study period 
08	Non-compliance with randomized medication (compliance category of under compliant or over compliant)  during the primary efficacy evaluation period, based on eCRF randomized medication exposure and compliance forms

**NOTES:**

[1] Evaluable Hgb values are described in Section 15.6.3.

[2] Prohibited medications include strong inhibitors of CYP2C8 (e.g., gemfibrozil) and strong inducers of CYP2C8 (e.g., rifampin/rifampicin), not include erythropoietin (e.g., epoetin/ darbepoetin alfa/ epoetin beta pegol, excluding darbepoetin alfa supplied by GSK).

[3] See Section 15.6.2; Over compliant: <80%, compliant: ≥80% and ≤120%, over compliant: >120%

CONFIDENTIAL

201754

15.2. Appendix 2: Schedule of Activities

15.2.1. Protocol Defined Schedule of Events

Phase	Screening	Treatment															
Visit	-4~-2 	Day 1	2	4	6	8	10	12	14	16	18	20	22	24	26	28	
All assessments pre-dialysis, unless noted.																	
Allowance range (days)	±3	-	±3	±3	±3	±3	±3	±3	±3	±3	±3	±3	±3	±3	±3	±3	
Informed consent	X																
Inclusion/exclusion criteria	X	X															
Medical history, demography, height, weight 	X																
IWRS call	X	X	X	X	X	X	X	X	X	X	X	X	X	X	X	X	
Study medication dispensing 		X	X	X	X	X	X	X	X	X	X	X	X	X	X	X	
Study treatment compliance			X	X	X	X	X	X	X	X	X	X	X	X	X	X	
Vital signs (before and after dialysis) 	X	X		X						X						X	
Ophthalmology 	↔							↔									
ECG	X													X			
HemoCue Hgb	X	X	X	X	X	X	X	X	X	X	X	X	X	X	X	X	
Hematology	X	X		X		Hgb only		Hgb only		X		Hgb only		Hgb only		X	
Clinical chemistry	X	X		X						X						X	
Pregnancy test (serum hCG) 	X	X		X						X						X	
Estradiol, FSH 	X																
PK 								X						X			
Ferritin, TSAT	X	X		X						X						X	
Serum iron, TIBC, UIBC, serum transferrin, hepcidin		X		X						X						X	
iPTH		X														X	
HR-QoL (SF-36, EQ-5D-5L/ EQ-VAS)		X						X								X	
Genetics sample 		X															
AE assessment 	X 	↔															
Concomitant Medications Review		↔															

CONFIDENTIAL

201754

Phase	Treatment													Follow-up
	30	32	34	36	38	40	42	44	46	48	50	52	Early withdrawal 	
Visit														
All assessments pre-dialysis, unless noted.														
Allowance range (days)	±3	±3	±3	±3	±3	±3	±3	±3	±3	±3	±3	±3	-	±3
Informed consent														
Inclusion/exclusion criteria														
Medical history, demography, height, weight 														
IWRS call	X	X	X	X	X	X	X	X	X	X	X	X	X	
Study medication dispensing 	X	X	X	X	X	X	X	X	X	X	X	X		
Study treatment compliance	X	X	X	X	X	X	X	X	X	X	X	X	X	
Vital signs (before and after dialysis) 						X						X	X	X
Ophthalmology 														
ECG												X		
HemoCue Hgb	X	X	X	X	X	X	X	X	X	X	X	X		
Hematology		Hgb only		Hgb only		X		Hgb only		Hgb only		X	X	X
Clinical chemistry						X						X	X	X
Pregnancy test (serum hCG) 						X						X	X	X
Estradiol, FSH 														
PK 														
Ferritin, TSAT						X						X	X	
Serum iron, TIBC, UIBC, serum transferrin, hepcidin						X						X	X	
iPTH												X		
HR-QoL												X	X	
Genetics sample 														
AE assessment 	←-----→													
Concomitant Medications Review	←-----→													

1. Body weight is measured after dialysis.
2. Daprodustat/placebo will be dispensed once every 4 weeks, and darbepoetin alfa/placebo will be dispensed once every 2 weeks
3. If a subject visit the study site only to receive study medication, only the IWRS call, study medication dispensing, and study medication compliance will be required.
4. At visits without dialysis, only one measurement of each parameter will be obtained.
5. Ophthalmology exams should be conducted at the following time points.

**CONFIDENTIAL**

201754

6. Screening: anytime after consenting and prior to first dose of study medication (Day 1)
7. Week 12: window from weeks 10-14 (inclusive)
8. End of study: window from weeks 48-52 (inclusive)
9. Early study medication discontinuation: withdrawal eye exam as close to the last dose as possible (the repeat exams are not required if one has been performed within the 2 prior weeks).
10. Performed in females of childbearing potential.
11. Measured in female subjects only to determine the menopausal status (see Section 5.1 in protocol.)
12. See Table 11 in protocol.
13. Informed consent for optional Genetic research should be obtained before collecting a sample (see Section 7.6 in protocol.).
14. See Section 7.4.1.1. in protocol. The interval between screening and Day 1 should be 4 weeks in subjects treated with epoetin beta pegol every 4 weeks or darbepoetin alfa every 4 weeks in the prior ESA therapy.
15. Only SAEs assessed as related to study participation or a GSK product are collected.
16. For withdrawn subjects, specified assessments should be done wherever possible.

### 15.3. Appendix 3: Assessment Windows

All data will be reported according to the nominal visit date for which it was reported (that is, no visit windows will be applied during dataset creation). Permissible range at each visit was specified in time & event table (See [Appendix 2](#)). Records in the eCRF unscheduled visit will not be slotted to a particular time point, but remain as unscheduled if they are either summarized or listed unless otherwise specified.

Regarding the visits where only HemoCue Hgb is available (i.e., Week 2, Week 6, Week 10, etc. See [Appendix 2](#)), the Hgb values will not be used for any analyses but presented in the listing unless otherwise specified.

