6.4.2.2. Maintenance Dose

From Weeks 2 to 52, dose interruptions or adjustments will be performed within the maintenance dose range of $10\sim60~\mu g$ (Table 8) according to the dose adjustment algorithm (Table 9) so that the HemoCue Hgb value measured every other week will achieve or remain within the target range (10.0-12.0 g/dL). Dose adjustments will be made once every 2 weeks. If any of the one-step dose reduction criteria is met during treatment at the minimum maintenance dose ($10~\mu g$), treatment should be interrupted (and placebo administered); once the one-step dose increase criteria are met, treatment at $10~\mu g$ will be resumed. If the one-step dose increase criterion is met during treatment at the maximum maintenance dose ($60~\mu g$), treatment at $60~\mu g$ should be continued.

Table 8 Maintenance dose of darbepoetin alfa

Dose level	1	2	3	4	5	6
Darbepoetin alfa (once weekly)	10 μg	15 μg	20 μg	30 μg	40 μg	60 μg

Table 9 Dose adjustment algorithm (darbepoetin alfa)

Hgb (g/dL)	Treatment
>13.0	Interrupt treatment (and administer placebo) until Hgb decreases to less than
	12.0 g/dL, and resume treatment at the one lower dose level
	[If interrupted (and placebo administered) at 10 μg, resume treatment at 10 μg
	after the one-step dose increase criterion is met]
\geq 12.0 and \leq 13.0	One-step dose reduction
\geq 10.0 and <12.0	Continue treatment at the current dose level*
≥7.5 and <10.0	One-step dose increase**
<7.5	Discontinue treatment permanently*** and initiate another appropriate treatment

^{*} If an increase of 1 g/dL is observed in 2 weeks, the dose will be reduced to the one-step lower dose level.

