7.3. Efficacy

Efficacy will be assessed according to the Time and Event Table (Table 10).

Hgb concentrations measured by the central laboratory will be mainly used for efficacy assessment. GSK will supply a point-of-care Hgb analyzer (HemoCue) to each site for rapid and convenient measurement of Hgb and to ensure consistency of Hgb measurements across all sites participating in the study. Assessment for Hgb concentrations via HemoCue will be used for eligibility (Section 5.1), permanent discontinuation of study treatment (Section 5.4), and dose adjustment criteria (Section 6.4). In addition, assessments of iron metabolism parameters used for exploratory assessment is outlined with specific procedures in Section 7.4.7.

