**NOTES :**

- T = Table, F = Figure, L = Listing, Y = Yes display generated.
- Stats Analysis = Represents TFL related to any formal statistical analyses (i.e. modelling) conducted.
- Summary = Represents TFL related to any summaries (i.e. descriptive statistics) of the observed raw data.
- Individual = Represents FL related to any displays of individual subject observed raw data.

[1] A summary will be produced for only daprodustat group

[2] <=-2, >-2 to -1, >-1 to 0, >0 to 1, >1 to 2, and >2 g/dL. In addition, within ±1 g/dL and over ±2 g/dL

[3] Not only within the target range, but also with above and below target range will be assessed.

[4] Rosendaal method will be used (See Section 15.6.3).

[5] On-therapy Hgb values observed at scheduled visits will be included in a summary. On-therapy Hgb values observed at unscheduled visits will be included if specified (See Section 7.3.2).

[6] Summaries for dose adjustment will based on HemoCue Hgb values including those of unscheduled visits.

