**7.3.2. Summary Measure**

Hgb at each assessment visit

The values will be summarized using mean, standard deviation, 95% CI, minimum, P25, median, P75, and maximum at each assessment visit by treatment group. Graphical summaries will be provided using mean and 95% CI over time. This will also be summarized by prior ESA type, prior ESA dose, and ERI subgroup.

Change from baseline at each assessment visit

The values will be summarized using mean, standard deviation, 95% CI, minimum, P25, median, P75, and maximum at each assessment visit by treatment group. Graphical summaries will be provided using mean and 95% CI over time. This will also be summarized by prior ESA type, prior ESA dose, and ERI subgroup.

Number (%) of subjects by Hgb change from baseline category at Week 4 - daprodustat

The number and percentage of subjects within each category will be provided only for daprodustat group and the categories will be classified into 6 (i.e., ≤-2, >-2 to -1, >-1 to 0, >0 to 1, >1 to 2, >2 g/dL). In addition, ‘within ±1 g/dL (i.e., ≤-1 and ≥1)’ and ‘over ±2 g/dL (i.e., <-2 and >2)’ categories will be provided. This will also be summarized by prior ESA type, prior ESA dose, and ERI subgroup.

Number (%) of subjects with Hgb within the target range at each assessment visit

The number and percentage of subjects with Hgb within, above and below the target range will be summarized at each assessment visit by treatment group. Graphical summaries over time will also be produced.

Time (%) in the Hgb target range during the primary efficacy evaluation period

The time (weeks and percentage) within/above/below the target range will be summarized by treatment group using mean, standard deviation, minimum, P25, median, P75, and maximum. Treatment differences (daprodustat – darbepoetin alfa) and the associated 95% CIs for the time (weeks and percentage) within the target range will also be provided. See Section 15.6.3 for details.

Number (%) of subjects who have an Hgb level of less than 7.5 g/dL

The number and percentage of subjects who have an Hgb level of less than 7.5 g/dL during the treatment period will be summarized by treatment group. On-therapy Hgb values observed in both scheduled and unscheduled visits will be included in the summary.

Number (%) of subjects who have an Hgb increase of more than 2.0 g/dL over any 4 weeks

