**Hgb Increase of More than 2.0 g/dL over Any 4 Weeks**

- For this reporting purpose, Hgb values from central laboratory will be used as previously described.
- A subject who has at least one record with Hgb increase of more than 2.0 g/dL over any 4 weeks will be counted and all episodes will be listed.
- Hgb increase will be calculated for scheduled visits between Day 1 and Week 52 if available (i.e. Week 4 Hgb - Day 1 Hgb, Week 8 Hgb - Week 4 Hgb, ...)

Illustration of calculation (example in case of Week 12 missing, until Week 24 visit)

Hgb (g/dL)	Lab Date	Study Day	Visit	Hgb increase
9.1	01FEB2017	1	Day 1	Not calculated
9.8	02MAR2017	30	Week 4	0.7
11.9	02APR2017	61	Week 8	2.1
12.6	07JUN2017	127	Week 16	Not calculated
12.7	08JUL2017	158	Week 20	0.1
12.3	02AUG2017	183	Week 24	-0.4

- Odds ratio and its 95% CI will be obtained using the same statistical model described in Section 7.2.5.
- When the odds ratio is undefined, it will not be presented.

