## 16. REVISION HISTORY

Note that minor wording changes are not included in below.

Reporting and Analysis Plan_201754_Amendment_Final_V1.1 [06-Aug-2018]		
Section # and Name	Description of Change	Brief Rationale
4 Analysis Populations 15.3 Appendix 3: Assessment Windows	It has been clarified that Hgb assessments at HemoCue visits (Week 2, 6, 10, ...) will not be included in the analysis.	Clarification
5.4.2 Examination of Subgroups	Subgroup definitions for ERI and period of time on dialysis were refined.	It would facilitate review of subgroup results
6 Study Population Analyses 15.10.4 Table of Contents for SAC Deliverable	Some modifications were made for study population displays as below: 1. Added 2 listings; subjects excluded from any population and subjects excluded from per-protocol population 2. Removed a summary of race and racial combination based on ITT population. 3. Added a separate listing of study specific baseline characteristics	1. It would facilitate review of results of populations analyzed. 2. Safety population would be sufficient to be assessed 3. It would facilitate review of results of baseline characteristics.
6.2 Planned Summary Display Details	Clarifications has been made to the way to display of exposure and treatment compliance.	Clarification
7.1 Primary Efficacy Analyses 15.10.4 Table of Contents for SAC Deliverable	Added tables of the tipping point analysis	It would facilitate review of tipping point results.
7.1.6.3 Tipping Point Analysis	The number of imputations was reconsidered and a text was updated.	Modifications
7.2 Principal Secondary Efficacy Analyses	A method to construct 95% CI and a one-sided p-value for odds ratio has been specified in Section 7.2.5.1 Statistical Methodology Specification	Clarification

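### The SAP leaves open whether Hgb from the 13 HemoCue-only visits counts for the <7.5 and >13.0 g/dL endpoints, and tests the >2 g/dL rise on only 13 of 25 four-week windows

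*SAP*

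**What the plan says.** **Default rule.** For visits with HemoCue only, SAP 15.3 states that "the Hgb values will not be used for any analyses but presented in the listing unless otherwise specified". The SAP revision history (Section 16) describes the same change as clarifying that "Hgb assessments at HemoCue visits (Week 2, 6, 10, ...) will not be included in the analysis".

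**Endpoints below 7.5 and above 13.0 g/dL.** SAP 7.3.1 note [5], attached to both, says: "On-therapy Hgb values observed at scheduled visits will be included in a summary". SAP 7.3.2 repeats for each: "On-therapy Hgb values observed in both scheduled and unscheduled visits will be included in the summary". Neither text names the measurement source. SAP 15.6.3 makes the central laboratory value the general source, with the same-visit HemoCue value as a fallback when the laboratory value is missing. It also confirms that unscheduled visits enter these two summaries.

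**Rise above 2 g/dL over any 4 weeks.** SAP 15.6.3 says "Hgb increase will be calculated for scheduled visits between Day 1 and Week 52 if available". It uses laboratory values, and its worked differences are Week 4 minus Day 1, Week 8 minus Week 4, and so on. Protocol 9.4.3 and SAP 7.3.2 plan a between-arm estimate for this endpoint; the SAP gives it as an odds ratio with a 95% CI.

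**Role of HemoCue.** Protocol 7.3: "Assessment for Hgb concentrations via HemoCue will be used for eligibility (Section 5.1), permanent discontinuation of study treatment (Section 5.4), and dose adjustment criteria". Under Protocol 5.4, a confirmed HemoCue average below 7.5 g/dL leads to permanent discontinuation in both arms. Under Protocol 6.4.2.2, darbepoetin alfa is adjusted every 2 weeks "so that the HemoCue Hgb value measured every other week will achieve or remain within the target range". Under Protocol 6.4.1.2, daprodustat is adjusted or interrupted only on the 4-weekly reading.

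**The concern.** Two of these endpoints ask whether a subject ever crossed a threshold, and the third whether Hgb ever rose too fast. Such endpoints depend directly on which readings are searched. If SAP 15.3 governs, half of the scheduled readings are not searched, while unscheduled ones are. A subject permanently stopped on a Week 6 HemoCue value below 7.5 could then be absent from the <7.5 count. A darbepoetin alfa subject interrupted at Week 6 for a value above 13.0 could be back below 13.0 by Week 8 and never be counted. The corresponding daprodustat decisions are all taken at visits that do count.

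If SAP 7.3.1 and 7.3.2 govern instead, the Week 6 readings count. Two programmers could therefore produce different tables from the same plan. For the >2 g/dL rise the text is clear, but the calculation is narrower than the endpoint's name.

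**Working it through.** No figure stated in the plan bears on this point; the power statement concerns only the primary test. The check is a count from the visit schedule, followed by an illustration on assumed inputs.

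**1. Readings** (Protocol Table 10, repeated in SAP 15.2.1)
- Scheduled post-baseline HemoCue visits, Weeks 2, 4, …, 52: 52/2 = 26.
- Visits that also have laboratory Hgb, Weeks 4, 8, …, 52: 52/4 = 13.
- HemoCue-only visits, Weeks 2, 6, …, 50: 26 − 13 = 13 (50%), the same in both arms.

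**2. Four-week windows for the >2 g/dL rise**
- With readings at Day 1 and every 2 weeks, windows start at Weeks 0, 2, …, 48: 48/2 + 1 = 25.
- On the 4-weekly grid, they start at Weeks 0, 4, …, 48: 48/4 + 1 = 13.
- Never tested (Week 2–6, 6–10, …, 46–50): 25 − 13 = 12, and 12/25 = 48%.

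**3. Dose-decision visits before Week 52**

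| Arm | Decision visits | Of these, HemoCue-only |
|---|---|---|
| Darbepoetin alfa | Weeks 2, 4, …, 50: 25 | 13 (52%) |
| Daprodustat | Weeks 4, 8, …, 48: 12 | 0 |

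**4. Which action can an omitted reading trigger?**
- Below 7.5: permanent stopping in either arm. The dosing schedule creates no imbalance.
- Above 13.0: interruption in the darbepoetin alfa arm only.
- Rise above 2 g/dL over 4 weeks: for daprodustat, a one-step reduction decided on 4-weekly readings, which becomes an interruption only at the minimum dose. The darbepoetin alfa table has no 4-week rise rule.

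**5. Illustration with interruption feedback.** Assumed, not from the documents: mean 11 g/dL, between-subject SD 0.5, within-subject SD 0.8–1.0, 2-week correlation 0.70–0.85, and a fall of 0.3–0.6 g/dL per 2 weeks while interrupted. Both arms follow the same underlying process.
- Subjects with any value above 13.0 who are missed on the 4-weekly grid: about 20–27% for daprodustat and 34–40% for darbepoetin alfa. If interruption has no effect, both are about 21%.
- In one scenario (within-subject SD 0.8, correlation 0.70, fall 0.3), the 26-reading rate is 18.8% in both arms. The 13-reading rates are 13.8% for daprodustat and 12.1% for darbepoetin alfa, a gap of 1.7 points created by the counting rule alone.
- Subjects with a rise above 2 g/dL who are missed: about 35–49% in both arms, with an arm gap of about 1–13 points.

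**6. Sensitivity to the assumed spread** (no dosing feedback, so no arm difference can appear). With total SD 0.92–1.14, correlation 0.6–0.8 and mean 10.9–11.0, about 22–35% of subjects with a value above 13.0 and 31–45% of those with a value below 7.5 are missed. With total SD 1.5, correlation 0.6–0.9 and mean 11, the figures are about 6–17% and 10–30%. The protocol's only SD, 1.5 g/dL, is for the period mean, not for single readings.

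**The case against.** A reader might infer that these readings are barred from every analysis. The documents do not support that. SAP 15.3 allows exceptions. HemoCue values enter the dose-adjustment summaries (SAP 15.6.3) and the rule for thrombosis secondary to excessive erythropoiesis, which has a 2-week criterion (SAP 15.6.4). For <7.5 and >13.0, SAP 7.3.1 and 7.3.2 can be read as the exception, since SAP 15.3.1 lists Weeks 2, 6 and 50 among the analysis time points. The Hgb flowchart, which may settle the matter, is not shown. This stands: for these two endpoints the defect is an unresolved conflict, not a settled exclusion.

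A reader might also infer that all three endpoints miss readings unequally by arm. The number omitted is the same in each arm, the <7.5 stopping rule is common to both, and a >2 g/dL rise does not stop treatment. Only >13.0 has a clear mechanism for imbalance.

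Further points have weight:
- Protocol 7.3 makes the central laboratory the main source for efficacy, and the 4-weekly rise calculation is disclosed with a worked example.
- The readings are listed, and reasons for discontinuation are tabulated.
- Laboratory hematology is planned at early withdrawal. It is on-therapy only up to treatment stop date plus 1 day (SAP 15.4.1.1), so it may not recover every stopped subject.
- HemoCue is noisier. With an assumed error SD of 0.2–0.6 g/dL, pooling all 39 readings (13 laboratory + 26 HemoCue) gives 19–38% of subjects with any value above 13.0, against 16% on 26 error-free readings and 12% on laboratory readings. That argues against pooling, not against a second row.

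**Conclusion.** The point holds in three parts.

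1. For <7.5 and >13.0, the SAP gives two rules that disagree on 13 of 26 scheduled readings, and the readable text does not reconcile them.
2. If SAP 15.3 governs, readings that trigger stopping (either arm) or interruption (darbepoetin alfa) can go uncounted while unscheduled readings count. For >13.0 this would tend to undercount darbepoetin alfa and so work against daprodustat.
3. The >2 g/dL endpoint, which carries an odds ratio, leaves 12 of its 25 four-week windows untested whichever rule governs.

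The visit, window and decision counts follow from the schedule for a subject who completes treatment. The proportions of subjects missed do not: they rest on assumed variability, correlation and response to interruption, and they vary several-fold over plausible inputs. They show a direction, not an established bias in the between-arm comparison. All three endpoints are secondary and, under Protocol 9.3.3, complementary or exploratory without multiplicity adjustment. The primary and principal secondary analyses use the 4-weekly values and are untouched.

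**What to change.** In SAP 15.3, 7.3.2 and 15.6.3, write an explicit exception for the three endpoints:

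- **<7.5 and >13.0 g/dL:** add a row using one on-therapy value per scheduled visit (central laboratory where available, HemoCue at HemoCue-only visits), plus the unscheduled values already included.
- **>2 g/dL rise:** add a row using all HemoCue-to-HemoCue pairs 4 weeks apart, including Weeks 2–6, 6–10 and so on. Staying within one method keeps differences between devices out of the rise.
- **Both:** keep the laboratory-only 4-weekly result beside each new row and label it as such.

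The cost is SAP wording and a few table rows from data already in the eCRF. The downside is that single HemoCue readings are noisier and that more readings raise any count of subjects who ever crossed a threshold. The laboratory-only row makes both effects visible. No dosing or stopping rule changes.
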